3.4.3. Interim Analysis

An interim analysis may be conducted after approximately 50% of the planned patients have been enrolled. All study primary and secondary efficacy endpoints will be summarized for the interim analysis. The unblinding information dissemination during this interim analysis will be controlled and described in the Request to Unblind Treatment Assignment document to ensure the trial integrity. If conducted, the interim analysis for primary and secondary endpoints will test the significance at alpha level of 0.001, two-sided, and the alpha level for the final analysis of primary and secondary endpoints will be 0.049, two-sided, between an ISIS 757456 treated group and placebo. The overall type I error rate will be controlled at 0.1, two-sided.

3.5. Exploratory Analyses

The exploratory efficacy analyses will be conducted using statistical methods described in Section 3.2.1. ANCOVA model will be used for continuous endpoints, logistic regression model will be used for dichotomous endpoints using PPS and FAS.

- Comparison of absolute levels, change and percent change from baseline to each scheduled post-Baseline visit in angiotensin II, renin (Plasma renin activity [PRA]; direct renin), and urinary AGT will be conducted between each ISIS 757456-treated group and pooled-placebo group in the PPS and FAS.
- Comparison of absolute scores, change from baseline to each scheduled post-Baseline visit in SF-12 scores (8 domains, PCS, and MCS), and EQ-5D-5L (5 dimensions, VAS, and index score) will be conducted between each ISIS 757456-treated group and pooled-placebo group.

- Proportion of non-worsening from baseline to each scheduled post-Baseline PGI-C and PGI-S will be compared between each ISIS 757456-treated group and pooled-placebo group. PGI-C will be categorized by non-worsening and worsening, where non-worsening includes categories of "Much better", "A little better" and "No change". PGI-S will be categorized by non-worsening and worsening, where non-worsening defined as ≥ 0 point improvement in the change from baseline score. The adjusted odds ratio (each ISIS 757456-treated dose group vs. pooled-placebo group) with 95% CI from logistic regression model will be provided.
- Comparison of change from Baseline to Study Day 85 in daytime SBP and DBP from 24 hr ABPM will be conducted between each ISIS 757456-treated group and pooled-placebo group
- Comparison of change from Baseline to Study Day 85 in nighttime SBP and DBP from 24 hr ABPM will be conducted between each ISIS 757456-treated group and pooled-placebo group
- Comparison of change from Baseline to Day 85 in eGFR will be conducted between each ISIS 757456-treated group and pooled-placebo group
- Comparison of change from Baseline to Day 85 in UACR will be conducted between each ISIS 757456-treated group and pooled-placebo group
- Primary endpoint, selective secondary and exploratory endpoints will be also analyzed using a sub-population of patients with Baseline 24 hr ABPM SBP > 130
- POP-HSQ scores will be listed.

Additional POP-HSQ summaries and analysis will be conducted, details are described in POP-HSQ SAP. Other exploratory PK endpoints will be further described in the Section 3.6.

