10.6.5. Exploratory Analyses

The change and percent change from Baseline to each schedule post-Baseline visit in angiotensin II and renin (PRA; direct renin) will be compared between each ISIS 757456 treated group and pooled placebo group in PPS and FAS. The data will be analyzed in a similar way to the primary analysis.

Change from Baseline to each schedule post-Baseline visit in SF-12 scores (domain, physical component summary, and mental component summary) and EQ-5D-5L (dimension, visual acuity score, index score) will be compared between each ISIS 757456 treated group and pooled placebo group in PPS and FAS.

Proportion of improvement from baseline to each scheduled post Baseline in PGI-S and PGI-C will be compared between each ISIS 757456 treated group and pooled placebo group in PPS and FAS.

Proportion of each questionnaire over time in POP-HSQ will be compared between each ISIS 757456 treated group and pooled placebo group in PPS and FAS.

The analyses will be detailed in the SAP.

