3.2.8. Scoring of Questionnaires

EuroQoL-5 Dimensional 5-level Questionnaire (EQ-5D-5L)

EQ-5D-5L is a standardized measure of health status developed by the EuroQoL Group to provide a simple, generic measure of health for clinical and economic appraisal. The EQ-5D-5L consists of the EQ-5D-5L descriptive system and the EQ visual analog scale (VAS).

The EQ-5D-5L descriptive system comprises five dimensions (mobility, self-care, usual activities, pain/discomfort and anxiety/depression), and the response to each dimension is scored as: 1 = no problems/pain/anxious, 2 = slight problems/pain/anxious, 3 = moderate problems/pain/anxious, 4 = severe problems/pain/anxious, 5 = unable/extreme. Lower score indicates worsening of QoL.

The EQ VAS is used as a quantitative measure of health outcome as judged by the individual respondent. The EQ VAS records a self-rating of health status on a vertical VAS anchored at 100 (best imaginable health state) at the top and 0 (worst imaginable health state) at the bottom.

Additionally, the EQ-5D health state index score reflects how good or bad a health state is according to the preferences of the general population of a country/region will be derived and summarized. If any of five dimensions is missing, then the index value will be set as missing. The details of EQ-5D health state index score derivation algorithm is described in Appendix 1.

Patient Global Impression

Patient Global Impression of Severity (PGI-S) is a single-item scale instrument asking patients to rate the severity of their health condition on a scale of (1) none, (2) mild, (3) moderate, (4) severe, (5) very severe.

Patient Global Impression of Change (PGI-C) is a single-item scale, which aims to evaluate all aspects of patients' health and determine if there has been an improvement or not in the patients' overall change in health condition. Patients rate their change as (1) much better, (2) a little better, (3) no change, (4) a little worse, (5) much worse.

Power Over Pressure - Hypertension Specific Questionnaire (POP-HSQ)

The POP-HSQ (Schmider, et. al 2017) comprising questionnaire A and questionnaire B (what symptoms have you experienced in the last 4 weeks). In questionnaire A, patients rate their health state in part 1 to part 4 and their blood pressure management and impact in part 5 to part 7. In questionnaire B, patients provide the experienced symptoms' frequency and intensity.

Short Form (SF) -12

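### SAP 3.5 compares PGI-C and PGI-S between groups only as non-worsening, so the comparison of the proportion improved that protocol 10.6.5 names is not made

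*Combined protocol and SAP*

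**What the plan says.** Protocol 10.6.5 sets the comparison as improvement: "Proportion of improvement from baseline to each scheduled post Baseline in PGI-S and PGI-C will be compared between each ISIS 757456 treated group". The comparator is pooled placebo, and both analysis sets (PPS and FAS) are used. It leaves the detail to the SAP.

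SAP 3.2.8 gives PGI-C five ordered levels: "Patients rate their change as (1) much better, (2) a little better, (3) no change, (4) a little worse, (5) much worse". It describes the item's purpose as establishing whether the patient's condition has improved. PGI-S also has five levels, from none to very severe.

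SAP 3.5 specifies a different outcome: "Proportion of non-worsening from baseline to each scheduled post-Baseline PGI-C and PGI-S will be compared between each ISIS 757456-treated group", again with pooled placebo as comparator. For PGI-C, the top three levels (much better, a little better, no change) form one category and the two worse levels form the other. For PGI-S the rule is "non-worsening defined as ≥ 0 point improvement in the change from baseline score". The reported measure is fixed too: "The adjusted odds ratio (each ISIS 757456-treated dose group vs. pooled-placebo group) with 95% CI from logistic regression model will be provided". No improvement cut, shift analysis or ordinal analysis of either item is specified.

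The SAP revision history records that the PGI wording in Section 3.5 was updated in version 2.0 (1 July 2022). It gives no reason and does not mention protocol 10.6.5.

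The schedule in protocol Appendix A collects PGI-C only at Day 85, and PGI-S only at Day 1 and Day 85. Each item therefore yields one post-baseline comparison per dose.

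**The concern.** The two documents name different outcomes for the same items. Improvement separates patients who feel better from everyone else; non-worsening separates patients who feel worse from everyone else. The SAP keeps only the second, although the protocol names the first and the SAP's own description of PGI-C points to the first.

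At stake is whether the planned comparison can answer the protocol's question. If the drug makes some unchanged patients feel better and does not alter how many feel worse, the specified odds ratios will show nothing. The responses needed to show it will already have been collected.

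**Working it through.** **1. The plan's own figure.** The documents give no sample size, power, distribution or effect size for PGI. The only design figure that can be recomputed is the one for the primary endpoint in SAP 3.3.2: 43 per group, from a difference of 8 mmHg, SD 13 mmHg, two-sided 0.05 and about 80% power. The normal approximation gives n = 2(1.960 + 0.842)² × 13² / 8² = 41.5, so 42 per group. With the t distribution, power is 79.6% at 42 and 80.5% at 43, so 43 reproduces. It is used here only to fix the group size: 150 patients in three groups is 50 each, and 50 × 0.9 = 45 evaluable.

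**2. The two cuts side by side.**

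| | Protocol 10.6.5 (improved) | SAP 3.5 (not worse) |
|---|---|---|
| PGI-C success | levels 1–2 | levels 1–3 |
| PGI-S success | better by at least 1 point | change of 0 or better |

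The protocol gives no numerical cut for improvement; the one shown is the natural reading of the scales.

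**3. What the SAP cut can register.** Let p1 to p5 be the PGI-C proportions. Improved is I = p1 + p2; not worse is N = p1 + p2 + p3. Move a share d from level 3 to level 1 or 2. Then I rises by d, and N is unchanged because d leaves and re-enters the same sum. Each patient who moves keeps the same binary value, so the adjusted model sees no difference either. The non-worsening odds ratio stays at 1.00 whatever the starting distribution. The same holds for PGI-S with improved, zero and worse in place of the levels.

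**4. Illustration.** Assumed placebo split, much better to much worse: 10/20/55/10/5%, so I = 30% and N = 85%. There are 45 per arm, two-sided 0.05. Odds ratio = [pA/(1 − pA)] / [pP/(1 − pP)], where A is active and P is placebo. Power = Φ{[|pA − pP| − 1.96√(2p̄(1 − p̄)/n)] / √([pA(1 − pA) + pP(1 − pP)]/n)}, where p̄ is the mean of pA and pP.

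| Assumed drug effect | Improved | OR | Power | Not worse | OR | Power |
|---|---|---|---|---|---|---|
| (a) 20 points, no change to better | 30 v 50% | 2.33 | 49% | 85 v 85% | 1.00 | none beyond error rate |
| (b) 30 points, no change to better | 30 v 60% | 3.50 | 83% | 85 v 85% | 1.00 | none beyond error rate |
| (c) 20 points more improved, 5 fewer worse | 30 v 50% | 2.33 | 49% | 85 v 90% | 1.59 | 11% |
| (d) only worsening falls, by 10 points | 30 v 30% | 1.00 | none beyond error rate | 85 v 95% | 3.35 | 35% |

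Worked case (b): (0.60/0.40)/(0.30/0.70) = 1.500/0.429 = 3.50. With 43 to 50 per arm, improvement power is 47–53% in (a) and 81–87% in (b).

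**5. Does one method win in general?** Simulations of 3,000 to 4,000 trials per scenario, 45 per arm, with all distributions assumed and the ordinal comparison made by an unadjusted Wilcoxon test:

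| Scenario | Not worse | Improved | Ordinal |
|---|---|---|---|
| Placebo 10/20/60/8/2%, common OR 2.5 | 21–22% | 55–59% | 62–64% |
| Placebo 10/20/55/10/5%, worsening 15% to 5%, improvement unchanged | 39% | 5% | 11% |
| Placebo 10/20/60/8/2%, worsening 10% to 25%, improvement unchanged | 48% | 5% | 16% |

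Ranges in the first row are across separate runs. A common odds ratio of 2.5 means improved 30% v 52% (odds 0.429 × 2.5 = 1.071) and not worse 90% v 96% (odds 9 × 2.5 = 22.5). The ranking reverses when the effect lies on the worsening side.

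**The case against.** The strongest defence is that non-worsening is a coherent question here. The drug is added to at least three antihypertensives, and protocol 2.5.2 lists hypotension among the risks. The synopsis places patient-reported quality of life under the Safety Objective, although protocol 1.1.4 and SAP 1.2.4 list it as exploratory. Scenario (d) and the reversed rankings show that this cut detects effects an improvement cut misses. This stands, and it is why non-worsening should be kept. It does not explain why improvement was dropped, because neither document states a tolerability aim for these items.

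It is also fair to say that protocol 10.6.5 defers detail to the SAP, that the revision is logged, and that nothing here enters the testing sequence in SAP 3.4.2. These points limit the consequence. But exchanging improvement for non-worsening changes the outcome itself, and the log gives no reason.

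A reader might infer more than the documents support:

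- **That improvement will be invisible.** SAP 3.2.1 provides category counts with percentages for most data, and allows listings of CRF data. No PGI table is named, but one may appear. The gap is in the between-group comparison.
- **That non-worsening will sit at its ceiling, or the logistic model will meet an empty cell.** No passage says these patients are mostly without symptoms or will rarely report worsening. The premise cuts both ways: a patient rated none on PGI-S at baseline cannot improve.
- **That a null PGI result would be taken as no patient benefit.** SAP 3.5 also compares SF-12 and EQ-5D-5L scores, and refers POP-HSQ to a separate plan.
- **That an ordinal model should replace both cuts.** Its advantage depends on a common odds ratio across all cuts, which is an assumption.

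**Conclusion.** The concern holds as a mismatch between the protocol's named comparison and the SAP's specified one. The key result is exact and needs no assumed distribution: any movement between no change and better leaves the non-worsening odds ratio at 1.00. Under the assumed placebo split, the improvement odds ratio missed in this way is 2.33 to 3.50.

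Every power figure above is illustrative, because the documents contain no PGI distribution and the ranking of methods depends on where the drug acts. The figures support reporting both cuts; they do not show that one is superior. The point is minor: the endpoints are exploratory and no confirmatory claim rests on them.

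**What to change.** In SAP 3.5:

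- Add the between-group comparison of the proportion improved beside the non-worsening comparison. Define improved as much better or a little better on PGI-C, and as at least 1 point better on PGI-S. Report an adjusted odds ratio and 95% CI for each cut.
- Commit to a table of all five categories by arm for both items.
- State the reason for departing from protocol 10.6.5. If the aim of non-worsening is tolerability, say so.
- Optionally, add a proportional-odds analysis of the five categories as a supplement, with its assumption stated.

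The cost is SAP wording, with no new data and no change to visits. The downside is one more exploratory comparison per item, outside the testing sequence. With one post-baseline visit, two doses and two analysis sets (PPS and FAS), that is 1 × 2 × 2 = 4 additional odds ratios per item.

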2.5.2. Risk Assessment

The known potential risks to study participants associated with ISIS 757456 are elaborated on in the Guidance for the Investigator section of the Investigator's Brochure. Additional study associated risks are:

Table 1: Known Risks Associated with RAAS Blockade

Potential Risk of Clinical Significance	Summary of Data/Rationale for Risk	Mitigation Strategy
Hypotension	RAAS blockade may lower BP Duration of effect: Long half-life of the ASO Extent of effect: AGT is the most upstream molecule in RAAS pathway	Eligibility criteria exclude patients at enhanced risk and Weekly BP monitoring Monitoring and stopping rules in place for hypotension
Hyperkalemia	RAAS blockade is known to increase serum potassium	ISIS 757456 is expected to have less effect on the renal RAAS system (less elevation of serum potassium) than ACEi, ARB or direct renin antagonists Most likely to occur in patients with high serum potassium. Eligibility criteria excludes K+>5.1 mmol/L and patients on medications that may cause hyperkalemia unless on a stable dose at least 1 month prior to the Screening visit and no known history of hyperkalemia per Investigator judgement. Eligibility criteria exclude patients at enhanced risk Monitoring and stopping rules in place for hyperkalemia
ARF	RAAS blockade is known to cause ARF	Based on liver (hepatocyte) targeting via the GalNAc conjugation, ISIS 757456 is expected to have less effect on the renal RAAS system than ACEi, ARB or direct renin antagonists Monitor renal function closely

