8.6.2. Stopping Rules for Renal Function Test Results

- 1. Confirmed 30% decline in eGFR from Baseline eGFR values [eGFR should be calculated using the CKD-EPI creatinine equation (Levey et al. 2009)]
- 2. Confirmed proteinuria: Absolute UPCR value ≥ 1000 mg/g

The possible dosing re-initiation or follow-up schedule for any events meeting either of these criteria will be determined by the Investigator **in consultation with** the Sponsor Medical Monitor or designee.

At the discretion of the Investigator, a decision to hold or permanently stop study drug may be made based on lesser changes in these parameters observed in isolation or in association with other renal-related abnormalities.

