3.2. General Overview of Analyses

3.2.1. Statistical Methods

The study outcomes will be summarized by treatment group. Descriptive summary statistics including number of patients, mean, median, standard deviation, standard error of mean, 25th percentile, 75th percentile, minimum, and maximum for continuous variables, and counts and percentages for categorical variables will be provided to summarize most data. The efficacy endpoints will be assessed on the full analysis set (FAS) and per-protocol set (PPS) with the latter being the basis for the primary efficacy analysis. The safety analyses will be performed on the Safety Set. Pharmacokinetic analysis will be conducted in the PK Set.

All planned analyses will compare each ISIS 757456 treatment group to pooled placebo.

All statistical tests will be conducted using 2-sided tests with 5% Type I error rate unless otherwise stated. P-values will be provided to assess the null hypothesis that there is no statistical difference between an ISIS 757456 treatment group and pooled placebo in study endpoints. The stratification factor (screening eGFR status [<60 vs. ≥ 60 mL/min/1.73 m²]), treatment received, and baseline measure are included in the Analysis of Covariate (ANCOVA) model as independent variables. For the continuous endpoints, the ANCOVA model will be applied or Van Elteren test with treatment and randomization stratification factor if the data departs substantially from normality. The normality assumption will be assessed by the Shapiro-Wilk test based on the residuals from ANCOVA modeling. Least Square mean (LSM) difference with 95% CI and p-values between treatment groups in study endpoints will be provided based on ANCOVA model. For the dichotomous endpoints, logistic regression model with treatment, randomization stratification factor and baseline measure (SBP) as independent variables will be used instead.

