3.2.2. Subject Population Analyzed

The following analysis populations are defined for this study:

- Full Analysis Set (FAS): All randomized patients who have received at least 1 injection of Study Drug (ISIS 757456 or Placebo) and who have at least 1 post-Baseline primary efficacy measurements.
- Per Protocol Set (PPS): All FAS patients who received at least 10 of the 12 doses of Study Drug, did not alter antihypertensive medications during the Treatment Period and prior to Study Day 85, and have no significant protocol deviations that would be expected to affect efficacy assessment. Significant protocol deviations are defined as those deviations from the protocol likely to impact the perceived efficacy and/or safety of study treatments, for example, other antihypertensive medication usage compliance during the study. After all data are entered, reviewed, and queried, the database is closed and sent to clinical group for review and identification of significant protocol deviations before unblinding.
- Safety Set: All patients who are randomized and receive at least 1 dose of Study Drug.
- Pharmacokinetics (PK) Set: All patients who are randomized and receive at least 1 dose of ISIS 757456 and have at least 1 evaluable PK sample.

In addition to the above analysis sets, it is recognized that some data displays will be provided for the number of patients in "All Screened", "Screening Failures" and "All Randomized" but no data analysis will be executed in these populations. A by-patient listing based on all randomized will be provided.

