3.2.3. Handling of Missing Data

Unless otherwise specified, missing values will not be imputed.

Patients with missing data for a scheduled assessment time point will be excluded from the summary for that time point.

Number of patients with missing data and missing data related to COVID-19 public health emergency may be provided.

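### The committed between-arm eGFR comparison rests on Day 85 alone, and its per-protocol version can drop patients whose eGFR fall ended their treatment

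*Combined protocol and SAP*

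**What the plan says.** **The comparison.** SAP 3.5 plans this: "Comparison of change from Baseline to Day 85 in eGFR will be conducted between each ISIS 757456-treated group and pooled-placebo group". The bullet names no analysis set. The opening of SAP 3.5 supplies it: ANCOVA for continuous endpoints and "logistic regression model will be used for dichotomous endpoints using PPS and FAS". The same section compares angiotensin II, renin and urinary AGT at every scheduled visit, so restricting eGFR to Day 85 is a choice.

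**The sets.** SAP 3.2.2 limits the PPS to "All FAS patients who received at least 10 of the 12 doses of Study Drug", with further conditions. The FAS has no dose minimum: it takes randomized, dosed patients "who have at least 1 post-Baseline primary efficacy measurements". SAP 3.2.3 does not impute: "Patients with missing data for a scheduled assessment time point will be excluded from the summary for that time point".

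**The renal rule.** Protocol 8.6.2 lists "Confirmed 30% decline in eGFR from Baseline eGFR values" as a stopping criterion. Protocol 8.6 labels the renal rules temporary, and 8.6.2 allows for dosing to restart. Protocol 8.5 (re-dosing guidance) and 8.8 make discontinuation permanent when the criteria are met.

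**Why the kidney matters here.** Table 1 in Protocol 2.5.2 states "RAAS blockade is known to cause ARF". Amendment 4 lowered the eGFR exclusion limit to 30.

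**The safety side.** SAP 3.2.1 states "The safety analyses will be performed on the Safety Set". SAP 3.7.3 tabulates the number and percent of patients with a confirmed 30% eGFR decline at any post-baseline time. It draws on central and local results, and SAP 3.2.1 adds unscheduled ones. A value that was never retested is presumed confirmed.

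**The concern.** A stopping rule defined on the outcome and an analysis set defined by doses received make a poor pair. A patient whose eGFR falls far enough early in treatment can be taken off drug, miss the dose minimum and leave the PPS because of that fall. The PPS mean then describes patients who tolerated the drug. If more active than placebo patients are lost this way, the contrast moves toward no renal effect.

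The second weakness is the single time point. Appendix A schedules chemistry at Days 15, 29, 43, 57, 71 and 85, and its footnote 7, attached to that panel, names eGFR. On-treatment values should therefore exist, but the committed comparison uses only the last. A repeated-measures model is optional in SAP 3.2.1 and is firmly promised only for the primary endpoint (SAP 3.3.1).

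Renal sparing is part of the stated rationale for the drug (Protocol 2.2 and 2.5.1). A reassuring per-protocol Day 85 result could be read as support for it, although the set may leave out patients who count against it.

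**Working it through.** **1. The plan's own figure.** No figure is given for the eGFR comparison. The nearest is 43 per group for SBP. A two-sample t calculation with difference 8, SD 13 and two-sided 0.05 gives 79.6% power at 42 per group and 80.5% at 43, so 43 reproduces. With 150 randomized, each dose arm has 150 × 1/2 × 2/3 = 50 and pooled placebo has 2 × 150 × 1/2 × 1/3 = 50. After 10% dropout, 50 × 0.9 = 45 remain. These sizes are used below.

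**2. Doses received at a renal stop.** Doses are weekly from Day 1, so the count through Day d is (d − 1)/7 + 1. Assume that day's dose is given before the result returns and that dosing does not restart. Gap = 85 − d. Drug remaining = 0.5^(gap/half-life), with the 2 to 4 week half-life in Protocol 2.3.4.

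| Chemistry day | Doses | Meets 10-dose rule | Days to nominal Day 85 | Half-lives | Drug remaining |
|---|---|---|---|---|---|
| 15 | 3 | no | 70 | 2.5–5 | 18–3% |
| 29 | 5 | no | 56 | 2–4 | 25–6% |
| 43 | 7 | no | 42 | 1.5–3 | 35–13% |
| 57 | 9 | no | 28 | 1–2 | 50–25% |
| 71 | 11 | yes | 14 | 0.5–1 | 71–50% |

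A temporary hold can have the same effect: three missed weekly doses leave 12 − 3 = 9.

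**3. Which value is Day 85 after an early stop.**
- The Synopsis and Appendix A footnote 9 place the Day 85 procedures at discontinuation or early termination. Protocol 8.8 puts the early termination procedures ideally within 2 weeks of the last dose. At 14 days, 50% to 71% of drug remains.
- Protocol 6.1.3 also has early terminators return on Study Day 85, which gives the gaps in the table.
- SAP 3.2.1 assigns values by visit label and averages values that share a label.

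If both visits carry the label, a patient at −30% at discontinuation and fully recovered at the later visit enters as (−30 + 0)/2 = −15%.

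**4. Size, by illustration.** Assume a fraction f of an active arm stops early on the rule, each loses exactly 30%, the other patients do not change, and no placebo patient stops. Mean decline absent from the PPS = f × 0.30 × baseline.

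| f | Baseline 60 | Baseline 75 | Expected stops per 50 |
|---|---|---|---|
| 2% | 0.36 | 0.45 | 1 |
| 5% | 0.90 | 1.12 | 2.5 |
| 10% | 1.80 | 2.25 | 5 |

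As a yardstick, an assumed SD of 9 with 45 per arm gives SE = 9 × √(2/45) = 1.90, so the range is 0.36/1.90 = 0.2 to 2.25/1.90 = 1.2 standard errors. The FAS loses none of this if patients are measured before recovery, half if half has recovered, and all of it if recovery is complete.

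**5. What the Safety Set adds.** The SAP 3.7.3 table would still show every one of these patients in the arm where they occurred. It would not show average falls short of 30%. The by-visit chemistry summary may show those descriptively, but the Appendix B analyte list is not visible, so eGFR reporting there is likely rather than confirmed. Neither output has a planned between-arm difference or interval.

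**The case against.** The strongest reply is that the plan already guards against the serious error. The Safety Set table counts confirmed 30% declines by arm, at any time, under the same criterion as the stopping rule. The FAS comparison stands beside the PPS one and has no dose minimum. The comparison is exploratory. The Synopsis reports that no renal stopping rule was met in either completed Phase 2 trial.

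Much of this stands, and it rules out three stronger readings that a reader might infer.

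- *That renal stoppers vanish from the comparison.* This applies to the PPS only. In the FAS they stay if they have a value labelled Day 85. A stop on the Day 71 sample does not breach the dose rule.
- *That they are measured after washout.* The documents do not settle this. One set of provisions puts the measurement at discontinuation; only the nominal Day 85 visit would fall several half-lives later.
- *That the trial as a whole understates renal harm.* The Safety Set table contradicts this. Its baseline is the last pre-dose value, whereas the stopping rule averages two pre-dose tests, so the patients may not match exactly, but the group is not hidden.

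The Phase 2 experience is weaker reassurance. The two trials enrolled 25 and 26 patients randomized 2:1, so about 34 received drug, at 80 mg for 6 or 8 weeks. Zero events in 34 has a one-sided 95% upper limit of 1 − 0.05^(1/34) = 8.4%. The 2% and 5% rows are compatible with that record; the 10% row lies above it.

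What the reply does not answer is that the only committed treatment contrast on eGFR uses one visit and, in one of its two sets, a population that the outcome itself can shape.

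**Conclusion.** The point holds in a limited form. The PPS eGFR comparison is open to selection on the outcome and can be biased toward no renal effect. Neither version is committed to use the Day 15 to 71 values. The Day 85 value is undefined for early terminators.

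Under the stated assumptions the PPS would miss 0.4 to 2.3 mL/min/1.73 m² of mean decline. Event rates, baseline and the 30% loss are all assumed. Placebo stops would shrink the bias in the contrast, and with no renal stops it is zero. The number leaving the PPS also depends on whether the renal rule is temporary or permanent, on which the protocol disagrees with itself.

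It is tempting to extend the argument to the Day 85 UACR comparison. The documents do not show that it carries over: the renal rule uses eGFR and UPCR, not UACR, and the UACR sampling days are not visible.

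This is a worthwhile, inexpensive improvement to the SAP. It does not show that the safety reporting fails.

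**What to change.** In SAP 3.5:

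1. Make the main eGFR comparison a repeated-measures model in the Safety Set, using all scheduled values to Day 85, with the between-arm difference and 95% CI at each visit. A scheduled value that triggered the renal rule then enters at its own visit.
2. Add the between-arm difference, with CI, in the proportion with a confirmed 30% decline.
3. Tabulate each patient's largest on-treatment fall by arm.
4. State which value counts as Day 85 for early terminators, and whether an early termination value and a nominal Day 85 value may be averaged.
5. Keep the PPS Day 85 result as supportive.
6. Treat UACR the same way only at visits where it is collected.

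Separately, the protocol sections that treat the renal rule as temporary (8.6, 8.6.2) and as permanent (8.5, 8.8) must be reconciled, because the answer determines who falls below 10 doses.

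The eGFR changes need SAP wording and a few extra exploratory outputs from chemistry already scheduled. They require no new visits.
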